10.6 Other Exploratory Analyses

10.6.1 Analysis of Influenza Antibody Titers

Variables Used for the Analysis

The analysis will require the following variables:

Variable	Source	Format/Notes
Influenza antibody titer values	Laboratory data	Influenza antibody titer values will be reported as “1/20”, for example. The denominator of the fraction will be used for analysis purposes.

Analysis

Changes in influenza antibody titers will be analyzed by comparison of means as well as proportions of subjects seroprotected (day 22 antibody titer ≥40) and seroconverted (day 22 antibody titer >4x baseline titer) at day 22. Means will be compared across treatment groups using a t-test and proportions will be compared across treatment groups using a Fisher’s exact test.

Analysis Population(s):	Confirmed Influenza

Derived Variables:	Mean change in influenza antibody titers from baseline to day 22: Mean of (day 22 influenza antibody titer – baseline influenza antibody titer) for each subject across treatment groups Proportion of subjects seroprotected at day 22: Number of subjects with day 22 antibody titer ≥ 40 divided by the total number of influenza-positive subjects with both baseline and day 22 data for each treatment group Proportion of subjects seroconverted at day 22: Number of subjects with day 22 antibody titer 4x the baseline titer divided by the total number of influenza-positive subjects with both baseline and day 22 data for each treatment group
--------------------	---

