8.4.2 Influenza Antibody Titer Analysis

For subjects with laboratory-confirmed influenza at baseline by culture or RT-PCR, changes in influenza antibody titers from baseline to day 22 will be analyzed by comparison of means as well as proportions of subjects seroprotected (day 22 antibody titer ≥ 40) and seroconverted (day 22 antibody titer $>4x$ baseline titer) at day 22. Means will be compared using a t-test, and proportions will be compared using a Fisher’s exact test.

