Change 3:	Page 19, Section 4.2, Exclusion Criteria Changed exclusion criterion # 15 from "Receipt of any dose of fNTZ, oseltamivir, zanamivir, peramivir, laninamivir, amantadine or rimantadine within 3 days prior to screening." to "Receipt of any dose of fN1Z, oseltamivir; zanamivir; peramivir, laninamivir, baloxavir, amantadine or rimantadine within 3 days prior to screening."
Action:	A revised protocol version 1.4 dated June 15, 2018 was generated
Amendment 3	
Purpose:	Update the protocol (1) to remove the exclusion criterion for influenza vaccination in order to have the studied population more accurately reflect the population affected by influenza and to ensure robust patient enrollment, (2) to clarify endpoint response definitions in accordance with the way patient diary questions are phrased, and (3) to make additional administrative updates.
Change 1:	Page 19, Section 4.2, Exclusion Criteria Deleted exclusion criterion 4, "Vaccination for seasonal influenza on or after (i) August 1, 2017 in the case of subjects enrolled during the 2017/2018 flu season in the Northern Hemisphere, (ii) February 1, 2018 in the case of subjects enrolled during the 2018 flu season in the Southern Hemisphere, or (iii) August 1, 2018 in the case of subjects enrolled during the 2018/2019 flu season in the Northern Hemisphere."
Change 2:	Page 25, Section 7.1, Electronic Data Entry Updated "Adverse events will be coded by data management using the Medical Dictionary for Regulatory Activities (MedDRA) version 15.1; medications will be coded by data management using the World Health Organization (WHO) Drug Dictionary." to "Adverse events will be coded by data management using the latest version of the Medical Dictionary for Regulatory Activities (MedDRA); medications will be coded by data management using the latest version of the World Health Organization (WHO) Drug Dictionary."

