7. STUDY DESCRIPTION

7.1 Study Objectives

The primary objective of this study is to evaluate the effect of nitazoxanide (NTZ) administered orally 600 mg b.i.d. with food for 5 days in reducing the duration of symptoms of influenza compared to that of a placebo.

A key secondary efficacy objective is to evaluate the effect of NTZ compared to placebo on time to return to ability to perform all normal activities.

Other secondary efficacy objectives include evaluating the effect of NTZ compared to placebo on:

- a) the proportion of subjects experiencing one or more complications of influenza including pneumonia, otitis media, bronchitis, sinusitis, worsening of pre-existing health conditions, systemic antibiotic use for infections secondary to influenza infection, hospitalization due to complications of influenza, and death; and
- b) the duration of symptoms of influenza during 21 days of follow up based upon the four FLU-PRO domains (Body/Systemic, Throat, Chest/Respiratory and Nose) that correspond to the seven symptoms included in the traditional patient-reported outcomes instrument (feverishness, myalgia, headache, fatigue, sore throat, nasal obstruction and cough).

Exploratory efficacy objectives include evaluating the effect of treatment with NTZ on the time to response for each FLU-PRO symptom, time to response for each FLU-PRO domain, time to resolution of febrile illness, time to return to usual health, and changes in viral titers from baseline to each of days 2, 3 and 7.

Other important objectives include evaluation of the safety of NTZ by analysis of adverse events and evaluation of the effect of nitazoxanide on influenza antibody response and evaluation of relationships between pharmacokinetics and clinical or virologic responses.

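### The Day 22 seroprotection comparison ignores the baseline titre, which dilutes any arm difference in that one exploratory antibody measure

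*SAP*

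**What the plan says.** One of the trial's further objectives is "evaluation of the effect of nitazoxanide on influenza antibody response" (SAP 7.1; Protocol section 2 has the same). SAP 10.6.1 serves it with three measures.

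- **Mean change**, derived as "Mean of (day 22 influenza antibody titer – baseline influenza antibody titer) for each subject across treatment groups" and compared by t-test.
- **Seroprotection**, worded as "proportions of subjects seroprotected (day 22 antibody titer ≥40", with the count "divided by the total number of influenza-positive subjects with both baseline and day 22 data for each treatment group".
- **Seroconversion**, given as "seroconverted (day 22 antibody titer >4x baseline titer) at day 22".

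For the last two, "proportions will be compared across treatment groups using a Fisher’s exact test". No stratification or adjustment is named.

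Protocol 8.4.2 plans the same set, a "comparison of means as well as proportions of subjects seroprotected" and seroconverted, with the same Day 22 cut-off of 40.

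The section sits under Other Exploratory Analyses in the SAP and outside the testing hierarchy of SAP 10.4. Amendment 3 (Protocol Appendix IV) was written in part "to remove the exclusion criterion for influenza vaccination". Vaccination status then became a stratum for the primary and key secondary tests, but not for the antibody tests.

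**The concern.** The question is whether the drug alters the antibody response to infection. A Day 22 status measure answers it only for subjects who still had the threshold to cross. Someone at 40 or more before dosing will usually still be there three weeks later on either treatment, and so adds a success to each arm without information on response. The SAP needs the baseline titre to define the denominator and then makes no further use of it.

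The effect is to pull the arm difference toward zero. If a small or non-significant difference in this measure were read as reassurance about the humoral response, the dilution would favour that reading. The share of such subjects may be higher among those enrolled after vaccinated subjects became eligible. The Day 22 percentage also cannot be read as a response rate.

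**Working it through.** **The plan's own figure.** The documents state no expected rate, margin, power or sample size for the antibody analysis, so there is nothing to reproduce. The group size is borrowed from the efficacy calculation (Protocol 8.1, SAP 7.3): 276 per arm with complete data. The inflation there is consistent, since 552 / (1 − 0.08) = 600. Using 276 for subjects with paired sera is an approximation.

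**Inputs**

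- From the documents: 1:1 allocation, two-sided 5% level (SAP 10.1), Fisher's exact test, denominator of all confirmed subjects with paired sera.
- Assumed, because the documents give no values: b, the share at 40 or more at baseline (20%, 40%, 60%); q, the share of the remainder reaching 40 by Day 22 (80% placebo, 65% NTZ); 99% of those at 40 or more staying there in both arms.

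**Dilution.** The Day 22 rate in an arm is P = 0.99b + (1 − b)q. The first term is the same in both arms and cancels, so the arm difference is (1 − b)(0.80 − 0.65). The share of placebo seroprotected subjects who were already there at baseline is 0.99b / P.

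| b | Placebo P | NTZ P | Difference | Already at 40 or more (placebo) |
|---|---|---|---|---|
| 20% | 0.198 + 0.640 = 0.838 | 0.198 + 0.520 = 0.718 | 12 points | 0.198 / 0.838 = 24% |
| 40% | 0.396 + 0.480 = 0.876 | 0.396 + 0.390 = 0.786 | 9 points | 0.396 / 0.876 = 45% |
| 60% | 0.594 + 0.320 = 0.914 | 0.594 + 0.260 = 0.854 | 6 points | 0.594 / 0.914 = 65% |

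**Power.** The Fisher and unstratified chi-square figures come from enumerating the two binomial distributions. The Cochran-Mantel-Haenszel (CMH) figures come from 200,000 simulated trials per case, without continuity correction. The restricted group sizes are 276 × 0.8 = 221, 276 × 0.6 = 166 and 276 × 0.4 = 110 per arm.

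| b | Fisher, all subjects (planned) | Chi-square, all subjects | Fisher, baseline below 40 | CMH by baseline titre |
|---|---|---|---|---|
| 20% | 91% | 93% | 93% | 94% |
| 40% | 78% | 81% | 84% | 86% |
| 60% | 55% | 60% | 66% | 68% |

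The chi-square column separates two effects. Part of the CMH gain comes from leaving Fisher's conservative test (55% to 60% at b = 60%). The larger part comes from using the baseline titre (60% to 68%).

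**The other two measures.** A simulation of two-fold titres, 276 per arm, assumed an impaired rise on NTZ: mean 2.0 against 2.5 log2 units, SD 1.6, smaller rises at higher baseline. With 17%, 50% and 73% at 40 or more at baseline, power was:

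- Day 22 titre of 40 or more: 0.54, 0.31, 0.13
- seroconversion at more than 4x: 0.77, 0.78, 0.76
- raw mean change: 0.55, 0.70, 0.77

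Only the seroprotection measure loses power as baseline titres rise.

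**The case against.** The strongest reply is that seroprotection does not stand alone. The same sentence of the SAP plans mean change and seroconversion, both against the subject's own baseline, and SAP 10.7 lists every titre by study day. A reader might infer that the plan would hide an impaired antibody response. The documents do not support that, and in the simulation above the other two measures do not lose power as baseline titres rise. They have loose ends of their own: seroconversion is more than 4x in the SAP's analysis text but 4x in its derived-variable row, and mean change is taken on raw titres. Neither removes the reference to baseline.

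A reader might also infer that Day 22 seroprotection largely measures prior immunity and vaccination. That is a statement about b, and the documents give neither the baseline titre distribution nor the vaccinated share. Under the assumptions used here it is true only when 0.99b exceeds 0.80(1 − b), that is b above 0.80 / 1.79 = 45%, so it fails in two of the three scenarios. Current-season vaccination was an exclusion until Protocol version 1.5 of January 2019, in a trial expected to run from December 2017 to April 2019, so that route affects only late enrolment.

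Nor does the earlier conclusion of no impairment rest on this measure. Protocol 1.2.4 and 1.2.5 base it on titre increases from baseline to Day 28, and 1.2.6 names no measure.

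Finally, the analysis is exploratory, carries no formal claim, and can be rerun later from data already collected. All of this stands, and it limits the point to one diluted measure. It does not answer why the baseline titre is left out of that measure.

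**Conclusion.** The point holds as a limited one. Day 22 seroprotection, as defined in SAP 10.6.1 and Protocol 8.4.2, understates any arm difference among subjects who could still cross the threshold, by about the factor 1 − b. With b between 20% and 60%, a 15-point difference appears as 12 to 6 points, and power falls from about 91% to 55%. Using the baseline titre brings it to between about 94% and 68%. The factor follows from the definition when retention is the same in both arms. The sizes rest on the assumed b, the 80% and 65% rates, 99% retention and 276 per arm.

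Under 1:1 randomisation this is dilution, not bias in favour of one arm. It concerns one of three exploratory measures and does not touch the primary or secondary analyses. Severity is low: a free improvement.

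**What to change.** In SAP 10.6.1, make one of two changes to the seroprotection comparison:

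- keep all subjects with paired sera and use a Cochran-Mantel-Haenszel test stratified by baseline titre (below 40, 40 or more); or
- compare the share reaching 40 or more at Day 22 among subjects below 40 at baseline, keeping Fisher's exact test.

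In either case, show the all-subject Day 22 percentages and the share at 40 or more at baseline by arm, as description.

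The stratified version has no material cost. The restricted version is simpler to read, but its denominator is smaller (221, 166 or 110 per arm in the scenarios above), so it restores the full difference and only part of the power. Either change is about one line of text. The baseline sample is already taken before the first dose (Protocol 5.2), and SAP section 6 allows revision until database lock.

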10.6.2 Population Pharmacokinetics Analysis

Variables Used for the Analysis

The analysis will require the following variables:

Variable	Source	Format/Notes
Day 3 tizoxanide (T) and tizoxanide glucuronide (TG) values	Laboratory data	
Demographic data	CRF	
Concomitant medications use	CRF	
Adverse events	CRF	

Analysis

Plasma concentrations of T and TG will be summarized descriptively for both treatment groups. Exploratory analyses will be conducted to evaluate relationships between plasma concentrations and age, race, gender, body weight, body mass index, concomitant medications (yes/no), changes in viral titer over time, Time to Symptom Response, and adverse events (yes/no). For continuous factors, the relationship with plasma concentrations will be assessed by Spearman’s correlation analysis and Pearson’s correlation analysis. For categorical factors, plasma concentrations will be compared among groups using the Kruskal-Wallis test.

Analysis Population(s):	Confirmed Influenza, NTZ-treated only
Derived Variables:	
 • Concomitant medications use: if any concomitant medication is used, then “yes”, otherwise “no” • Adverse events: if any adverse event is reported, then “yes”, otherwise “no” • Changes in viral titer over time: see section 10.5.5 • Time to Symptom Response: see section 10.2

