10.2.2 Analysis of the Primary Efficacy Parameter

The primary efficacy parameter, time to Symptom Response, will be derived as follows:

Event: Time of Symptom Response – time of the first dose
 Censored: Time of last symptom assessment – time of the first dose

If Symptom Response is achieved at the time of the first symptom assessment diary record, the subject will be excluded from the analysis.

If Symptom Response is not achieved prior to a subject’s last available diary assessment, but the criteria are met at the last available diary assessment with no evidence of symptom relief medication intake during that diary period, time of Symptom Response will be considered to have occurred at the start of the last daily diary period.

Time to Symptom Response for the NTZ treatment group will be compared to that of the placebo treatment group using a Gehan-Wilcoxon test stratified for (1) time from onset of illness to time of first dose of study medication (0-24, >24-≤36, or >36 hours from onset), and (2) vaccination status (Y/N). The comparison will be graphically depicted using Kaplan-Meier curves.

Analysis Population(s):	Confirmed Influenza
Derived Variables:	Event: Time of symptom response – time of the first dose Censored: Time of last symptom assessment – time of the first dose

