16.2.6.7	Listing of Time to Resolution of Acute Febrile Illness	Listing	Confirmed Influenza
16.2.6.8	Listing of Time to Return to Usual Health	Listing	Confirmed Influenza
16.2.6.9	Listing of Virology Data	Listing	Confirmed Influenza

Display Number	Title	Type	Analysis Population
16.2.6.10	Listing of Influenza Antibody Titer Data	Listing	Confirmed Influenza
16.2.7	Listing of Adverse Events	Listing	All Treated
16.2.8.1	Listing of Hematology Laboratory Results	Listing	All Treated
16.2.8.2	Listing of Serum Biochemistry Laboratory Results	Listing	All Treated
16.2.8.3	Listing of Urinalysis Laboratory Results	Listing	All Treated
16.2.8.4	Listing of Plasma Tizoxanide and Tizoxanide Glucuronide Results	Listing	All Treated
16.2.9.1	Listing of Vital Signs Data	Listing	All Treated
16.2.9.2	Listing of Physical Examination Data	Listing	All Treated

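### The exploratory PK analysis uses ordinary correlation for a right-censored time and restricts relations unrelated to influenza response to confirmed-influenza NTZ subjects

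*SAP*

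**What the plan says.** SAP 10.6.2 relates Day 3 tizoxanide and tizoxanide glucuronide concentrations to age, race, sex, weight, BMI, concomitant medication, change in viral titre, Time to Symptom Response and adverse events (yes/no).

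- **Method.** The rule is "For continuous factors, the relationship with plasma concentrations will be assessed by" Spearman and Pearson correlation. The only other method is for factors with categories: "For categorical factors, plasma concentrations will be compared among groups using the Kruskal-Wallis test".
- **The time variable.** It is taken over unchanged: "Time to Symptom Response: see section 10.2". SAP 10.2.2 gives a subject without a response a censored value: "Censored: Time of last symptom assessment – time of the first dose". Protocol 8.4.1 also treats such subjects as censored.
- **Population.** One population covers every relation: "Confirmed Influenza, NTZ-treated only". Table 14.2.13 in SAP Appendix II matches it. Protocol 8.4.3 plans the same relations and does not limit them to confirmed influenza.
- **Sampling.** Protocol 5.5 plans the Day 3 blood sample for each subject, subject to opt-out, and does not make it depend on the influenza result. Protocol section 3 keeps sites and subjects blind to virology until after day 22.

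**The concern.** A time in hours can only fall under the rule for continuous factors, so Time to Symptom Response goes to correlation. Correlation needs one number per subject, and a censored subject does not have one. If the censoring time is used as observed, a subject who leaves early looks like a fast responder. If censored subjects are dropped, those still unresolved at the end of follow-up are lost, and they are the slowest. Either choice can pull the estimated relation towards zero. The SAP makes neither, so the choice could be left until after unblinding.

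The population is a separate matter. Confirmed Influenza suits the relations with symptom response and viral titre. It is not needed to ask how concentration varies with body weight, or whether subjects with adverse events had higher concentrations. Influenza-negative NTZ subjects take the same tablets, are due the same sample and have adverse events recorded in the same way.

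At stake is the precision of descriptive PK evidence. Relating PK to clinical or virologic response is a stated objective in both documents. Concentration against adverse events is the only exposure-safety comparison planned.

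**Working it through.** SAP 10.6.2 states no figure to reproduce. The planning inputs behind the counts do reproduce.

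**Inputs from the documents** (protocol 8.1 and 5.5, SAP 7.3): 552 subjects for 90% power; 8% incomplete data; 600 confirmed subjects, 300 per arm; flu-positive rate 50% to 75%; 800 to 1,200 enrolled; at least 75% expected to complete the Day 2 and Day 3 visits.

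- 552 / (1 − 0.08) = 600, as stated.
- 600 / 0.75 = 800 and 600 / 0.50 = 1,200, as stated.

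**Population**

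1. All NTZ subjects at 1:1 randomisation: 300 / 0.75 = 400 to 300 / 0.50 = 600.
2. With a Day 3 sample, confirmed influenza: 0.75 × 300 = 225.
3. With a Day 3 sample, all NTZ: 0.75 × 400 = 300 to 0.75 × 600 = 450.
4. Share left out: 1 − 225/300 = 25% to 1 − 225/450 = 50%.
5. Standard-error ratio if all are used: √(225/300) = 0.87 to √(225/450) = 0.71, a cut of about 13% to 29%.

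The 75% completion rate is assumed equal by influenza status. It then cancels from steps 4 and 5. Step 5 also assumes similar spread in both groups.

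**Censoring** (simulation; all inputs in this paragraph are assumptions except 504 h, and the 8% borrows the plan's incomplete-data allowance). 225 subjects, 1,500 replicates per scenario, true log-scale correlation −0.30, lognormal times with median 150 h, and early dropout uniform over 24 to 504 h. Where some subjects are unresolved at 504 h, the spread of times is set to give that share. Mean Spearman correlation:

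| Early dropout | Unresolved at 504 h | Uncensored | Censored times used as observed | Censored subjects dropped |
|---|---|---|---|---|
| 0% | 25% | −0.286 | −0.280 | −0.208 |
| 8% | 0% | −0.285 | −0.278 | −0.284 |
| 8% | 10% | −0.286 | −0.279 | −0.245 |
| 8% | 25% | −0.290 | −0.280 | −0.213 |
| 20% | 0% | −0.286 | −0.270 | −0.283 |
| 20% | 25% | −0.286 | −0.270 | −0.214 |

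- Used as observed, the largest shrinkage is 1 − 0.270/0.286 = 5.6%.
- Dropped, it is 1 − 0.245/0.286 = 14% with 8% dropout and 10% unresolved, and 1 − 0.208/0.286 = 27% with no dropout and 25% unresolved.
- Log-scale Pearson behaves alike: with 8% dropout and 25% unresolved it is −0.303 uncensored, −0.284 used as observed and −0.225 dropped.
- Which handling is worse depends on the scenario. With early dropout and nobody unresolved, dropping costs subjects but hardly any correlation.

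**Would the alternative help?** A separate simulation (225 subjects, assumed lognormal times) gave power of 82% to 92% with censored times used as observed, 68% to 89% with censored subjects dropped, and 88% to 92% with a Cox model. Cox did not do materially worse in any scenario. Its gain over using censored times as observed was 0 to 6 points.

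**The case against.** - **Nothing confirmatory depends on this.** SAP 10.6.2 stands under other exploratory analyses, outside the hierarchy of SAP 10.4, with no hypothesis or power target. This stands, and it limits the weight of the point.
- **The attenuation may be trivial.** Also largely right if censored times are used as observed and censoring is modest. A check with 8% dropout over 48 to 504 h and medians of 120 to 200 h moved Spearman only from between −0.226 and −0.229 to between −0.221 and −0.224. A contributing subject must still be in the study at about 48 h to give the sample. SAP 10.2.2 also counts a response met at the last diary, which reduces censoring. Dropping censored subjects remains the costly choice, and the SAP does not rule it out.
- **A third handling exists.** SAP 10.3.1 assigns 504 h to subjects who discontinue without response. It is a sensitivity analysis of the primary endpoint and is not carried into SAP 10.6.2. It also makes every early leaver one of the slowest subjects, so it replaces one arbitrary value with another.
- **Confirmed Influenza fits the stated objective.** It does for response and titre, and should stay there. The documents do not say that the other relations are free of influenza status, so widening the population is a judgement. Showing those results by influenza status as well would meet the objection.

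A reader might infer that "Listing of Plasma Tizoxanide and Tizoxanide Glucuronide Results", which is display 16.2.8.4 and is set to All Treated, contradicts the analysis population. It does not. SAP 11.2 presents safety listings for all subjects as a matter of course, and table 14.2.13 agrees with SAP 10.6.2. A reader might also infer a large, established loss of power. The documents give no censoring rate, recovery-time spread or expected correlation from which to establish one. Nor is complete follow-up a fair comparator, since no method recovers what censoring removes.

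**Conclusion.** The point holds as a low-cost improvement to an exploratory analysis.

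- **Censoring.** Correlation is the wrong tool for Time to Symptom Response, and the handling of censored subjects is left open. The likely effect is a slight weakening of the relation under modest censoring. It is larger if many subjects are unresolved at 504 h and are dropped. Sizes and ranking rest on assumed medians, correlation and censoring rates.
- **Population.** The restriction appears only in the SAP and leaves out about 25% to 50% of NTZ subjects with a Day 3 sample for relations that do not concern influenza response. This rests on the plan's own flu-positive range and on equal PK completion by influenza status. For safety it concerns a single yes/no comparison.

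The primary and secondary efficacy conclusions are not touched.

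**What to change.** Amend SAP 10.6.2 before unblinding:

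1. **Time to Symptom Response.** Replace correlation with a Cox model on log trough concentration in confirmed-influenza NTZ subjects. Stratify by the SAP's analysis strata, which are onset-to-first-dose time and vaccination status; randomisation used onset time alone. A censoring-aware concordance measure is an acceptable alternative. State a rule for concentrations too low to log.
2. **Demographics, concomitant medication and adverse events.** Use all NTZ-treated subjects with a Day 3 sample, shown also by influenza status if wanted.
3. **Viral titre and symptom response.** Keep Confirmed Influenza.
4. **Appendix II.** Split table 14.2.13 to show the two populations.

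The cost is SAP wording and standard code. No new data, visits or samples are needed.
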